Patients will undergo daily nasal swabbing (dry cotton swab passed around the anterior nares and then immersed in viral transport medium (VTM). As discussed earlier, seasonal influenza virus is generally shed by adults for up to 5 days and young children for up to 10 days. There is some early evidence to suggest that viral shedding with H1N1 swine flu is occurring over a slightly extended time. In light of this we will attempt to undertake sampling daily for up to 10 days in children <13 years. In practice this will likely mean performing swabs daily on average 8 days in adults and 10 days in children <13 years.

We expect to collect 950 samples in total:

- Hospitalised adults: 25 patients, 1 sample a day for (on average) 8 days = 200
- Hospitalised children: 25 patients, 1 sample a day for (on average) 11 days = 275
- Adults in their own homes: 25 patients, 1 sample a day for(on average) 8 days = 200
- Children in their own homes: 25 patients, 1 sample a day for (on average) 11 days = 275

2. Surface Swabbing

The purpose of this is to establish the relationship between viral shedding and contamination of the environment with viable virus. The consortium is already heavily involved in HPA funded work concerned with virus survival, which is specifically looking at virus survival on fomites and the efficacy of household cleaning agents. The consortium therefore has particular expertise in this area and has already validated methods of environmental sampling.

To analyse such a relationship between viral shedding and environmental contamination, it will be necessary to ensure that only one person (the index case) is contributing to environmental shedding. Therefore it will be necessary to limit our sampling to those hospital patients who are in side rooms and those patients at home who are the only symptomatic members of that household. However, we recognise that over a period of sampling time (up to 10 days in adults, 12 in children) other members of a household may well develop symptoms. In this instance we would continue sampling (index case and surfaces) but would record the symptoms of all symptomatic individuals.

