It will be necessary to clean down surfaces following swabbing each day to remove viral genomic material, so that the following days swabs reflect the deposition of new material. This will preferably be done with a chlorine based agent but will depend on the surface. It may then be necessary to was the wash the cleaned surface with distilled water to remove any residue of cleaning agent that may affect virus that is subsequently shed upon it.

Samples will be taken every other day during the period of follow up, i.e. nasal swab one day, nasal swab + surface swabs on the next day. We will randomly allocate patients to have surface swabbing done on either days 1, 3, 5, 7, 9 and 11 or 2, 4, 6, 8, 10 and 12.

Samples will be taken by swabbing 2 cm² areas on selected surfaces from within the rooms housing patients. For consistency we have chosen the following surfaces though we will allow some discretion to be exercised by the researcher;

Hospital;

- Patient table (mid-point or nearest to midpoint)
- Patient line console (e.g. on/off button) / Nurse call button depending on circumstances
- Door handle
- Patient drinking receptacle (cup / glass)

Home;

Virus Shedding Study Protocol Version 1.2, 27AUG2010

Page 24 of 38

- Kitchen Fridge door handle+ kettle handle
- Lounge TV remote control (mid point on the back of the device), light switch
- Bathroom Tap + door handle
- Mobile phone

We expect to obtain 1875 samples in total:

- Hospitalised adults: 12.5 patients (we estimate that 50% of hospital patients will be in side rooms), 12 samples (3 samples every other day for 8 days) = 150
- Hospitalised children: 12.5 patients (we estimate that 50% of hospital patients will be in side rooms), 18 samples (3 samples every other day for 12 days) = 225
- Adults in their own homes: 25 patients, 24 samples (6 samples every other day for 8 days) = 600
- Children in their own homes: 25 patients, 36 samples (6 samples every other day for 12 days) = 900

Method of sampling:

Cotton / fibre tipped swabs to be dipped in tube containing 1.5 ml viral transport medium and then rubbed across 2 cm² area of surface in 6 different directions, applying even pressure. Swab to be broken off into tube containing SFM.

3. Air Particle Collection

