A two-stage bio aerosol cyclone sampler will be used to i) measure the quantity of influenza virus and ii) look for live virus in aerosol particles around patients. The sampling devices and accessory equipment have been loaned by NiOSH as previously mentioned and have been validated both in the UK and the US (see picture at appendix 2). The sampler draws in air at 3.5 litres/min and separates particles into three size fractions (>4, 1-4 and <1 micrometers). The particles are collected in falcon conical tubes containing VTM or on filter paper These fraction sizes are important because particles of less than 4 micrometers in diameter (aerosols) are capable of being inhaled and reaching the lower respiratory tract, where as particles >4 micrometers behave as droplets. It would therefore be interesting to know whether influenza, particularly viable influenza can be found in such particles as this would weight to premise that influenza can be transmitted by aerosols. In addition, by placing samplers at specified or consistent distances away from patients we can assess whether larger particles (droplets) can travel more than commonly accepted 4ft distance.

The samplers will run for 3 hours for each collection. They are powered by an air pump which does generate some noise but this is not excessively intrusive. They will be positioned in the following places;

 Hospital setting: One sampler will be placed within 4ft of the patient's bed, at chest height and within a 180 degree angle of the patients face. A further sampler will be placed at a distance of >7ft from the patients bed ideally against the wall opposite the patient, 150cm off the ground. Samplers will be mounted on drip stands.
 If a patient moves out of a side room we will continue nasal swabbing but will stop

If a patient moves out of a side room we will continue nasal swabbing but will stop environmental sampling.

- Household setting: We will only collect samples if we know that a patient will be relatively stationary for the duration of sampling, e.g. in bed. Samplers will be placed as above. Samples will be taken every other day during a patients follow up from the first day. We expect to have the use of 6 sampling devices but because of equipment and time constraints we will

not be able to perform air sampling around every patient. Over the course of the study we will aim to follow 16 patients.

Based on this we expect to obtain 480 samples in total:

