- Hospitalised adults: 4 patients, 4 sampling days (sampling every other day for 8 days), 6 samples each time (3 from each sampler) = 96
- Hospitalised children: 4 patients, 6 sampling days (sampling every other day for 12 days), 6 samples each time (3 from each sampler) = 144
- Adults in their own homes: 4 patients, 4 sampling days (sampling every other day for 8 days), 6 samples each time (3 from each sampler) = 96
- Children in their own homes: 4 patients, 6 sampling days (sampling every other day for 12 days), 6 samples each time (3 from each sampler) = 144

A sample patient schedule can be seen at appendix 2.

4. Stool Sample Collection

Detailed instructions will be provided explaining how to obtain a sample. We will ask the patient to empty their bladder first if possible. They will then place a collecting plate in the toilet bowl which will catch the stool. A sample can then be taken and put in the container. The remaining stool is then tipped into the toilet and flushed away. The plate is disposed of in a rubbish bag. Once the sample container has been securely capped, it should be placed in a specimen bag and kept in a small cooler box (which will be provided). Hand washing / hygiene measures will be stressed. Stool samples will be collected daily along with the other samples.

Sample Processing (stool samples dealt with separately – see below)

The generation of \approx 3,300 samples for both PCR and PA is a considerable amount of work requiring not just expertise but also significant laboratory resources, including time. Thus, it is not possible to generate results on all samples collected in a short period. We therefore propose to define a sample processing protocol based on results from the first few cases. It could include the following;

- If a patient tests negative for swine flu (as part of NHS care) we will exclude them from further study.
- Environmental swabs will not be processed if nasal swabs from a case are PCR negative.
- Environmental swabs will only be processed if nasal swabs from a case show a high viral load.
- Environmental swabs will not be processed for PA if nasal swabs from a case are PA negative.

Note; samples that are not processed rapidly will be retained for analysis in the future should this be of interest.

Transport and storage of participant samples

Transport

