11. STATISTICS

Proposed Sample Size

We will aim to recruit groups of about 25 patients with recent onset H1N1 influenza in each of the four main sub-groups identified under 'research methods'. Most statistical analysis will involve examining correlations between virus shedding and virus deposition in the environment. The figure below illustrates that sub-group sizes of 25, which also allow pooling of data by adults or children (50 per group) or the whole population gives high statistical power (>80%) to detect correlations of >0.55 in groups of size n=25, 0.4 in groups of size n=50, and 0.3 in groups of size n=100.

As regards the duration of virus shedding, these data will be primarily descriptive but it will be important to be able to make formal statistical comparisons of the duration of shedding between adults and children. However by pooling data into adults vs. children (n=50 per group) differences of 5 days (adults) vs. 6 days (children) (two tailed-test) could be detected with >80% provided that the coefficient of variation in shedding was 0.3 or less. For larger differences e.g. 5 days vs.7 days or 5 days vs. 8 days, the study is well powered to coefficients of variation up to 0.6.

Statistical Analysis

Virus Shedding Study Protocol Version 1.2, 27AUG2010

Page 28 of 38

We will perform a detailed descriptive analysis of the data. The symptom constellation of patients in the different groups will be presented. The mean (standard deviation, range) of the quantity of infectious virus in the patient, on surfaces and in the air will be plotted for each patient group and as a function of time since onset, symptom constellation and distance from source (when relevant). The mean (standard deviation, range) duration of shedding will also be plotted for each patient group and as a function of symptom constellation. For a better representation of inter-individual variation (which is expected to be important), we will also plot individual trajectories.

In a second stage, formal tests will be used to determine which outcomes are significantly associated / correlated. Statistical tests will also be implemented to compare the mean duration of shedding among children and adults as well as among mild and severe cases.

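### The >80% power for shedding-versus-environment correlations counts enrolled patients, but the sampling plan provides environmental data on fewer: a severe shortfall for hospital surface sub-groups and all air correlations, a modest one for pooled surfaces

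*Protocol*

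**What the plan says.** Section 11, Proposed Sample Size, sets the recruitment target: "We will aim to recruit groups of about 25 patients with recent onset H1N1 influenza in each of the four main sub-groups". It says what the numbers are for: "Most statistical analysis will involve examining correlations between virus shedding and virus deposition in the environment". It then allows for pooling, "which also allow pooling of data by adults or children (50 per group) or the whole population", and concludes that this "gives high statistical power (>80%) to detect correlations of >0.55 in groups of size n=25, 0.4 in groups of size n=50, and 0.3" at n=100. The Synopsis repeats the paragraph.

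Section 10, Study Procedures, says who will have environmental samples. Surface swabbing is limited to hospital patients in side rooms and to home patients who are the only symptomatic household member. The sample count uses "Hospitalised adults: 12.5 patients (we estimate that 50% of hospital patients will be in side rooms"), the same 12.5 for hospitalised children, and all 25 patients in each home group. For air, equipment and time limit coverage: "Over the course of the study we will aim to follow 16 patients". The count begins "Hospitalised adults: 4 patients, 4 sampling days" and gives 4 patients to each of the other three sub-groups as well.

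Section 11 gives no alpha or sidedness for the correlations. It mentions a two-tailed test only for the comparison of shedding duration.

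**The concern.** A correlation between nasal shedding and deposition needs both measurements on the same patient. The power paragraph puts in the number enrolled, while the sampling plan in the same protocol provides the environmental half of the pair for fewer patients. The paragraph makes no adjustment for this.

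Correlating shedding with surface and air contamination is primary objective (ii). Section 6 also uses the comparison of touched and respired environments to steer policy on hand hygiene against respiratory protection. Those two sides rest on 75 and 16 patients, yet one power statement covers both. A reader who takes that statement at face value could give a non-significant air or hospital-surface correlation more weight than it can bear.

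**Working it through.** **Inputs.** Target correlations and n (25, 50, 100) come from section 11. Patients with surface data (12.5, 12.5, 25, 25) and with air data (4 in each sub-group) come from section 10. Alpha is assumed to be two-sided 0.05, with one pair per patient.

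**Evaluable n.**
- Surfaces, per age group: 12.5 + 25 = 37.5. Overall: 2 × 37.5 = 75.
- Air, per age group: 4 + 4 = 8. Overall: 4 × 4 = 16.

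**Formulas (Fisher z).** Power = Φ(atanh(r)·√(n−3) − 1.96). Correlation detectable with 80% power = tanh(2.80/√(n−3)). The transforms are atanh(0.55) = 0.618, atanh(0.4) = 0.424 and atanh(0.3) = 0.310.

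**The plan's own figures.**
- n=25, r=0.55: Φ(2.900 − 1.96) = 82.7%
- n=50, r=0.4: Φ(2.904 − 1.96) = 82.8%
- n=100, r=0.3: Φ(3.048 − 1.96) = 86.2%

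All three exceed 80%, so the arithmetic is right for the n used. A simulation of the t-test for r gave 84.3%, 83.4% and 86.5%. The patients needed for 80% are 24, 47 and 85.

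**At the n that section 10 plans.**

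| Outcome and tier | n | r | Power | Detectable r at 80% |
|---|---|---|---|---|
| Surface, each hospital sub-group | 12.5 | 0.55 | Φ(1.906 − 1.96) = 48% | 0.72 |
| Surface, each home sub-group | 25 | 0.55 | 82.7% | 0.54 |
| Surface, each age group | 37.5 | 0.4 | Φ(2.488 − 1.96) = 70% | 0.44 |
| Surface, overall | 75 | 0.3 | Φ(2.626 − 1.96) = 75% | 0.32 |
| Air, each sub-group | 4 | 0.55 | Φ(0.618 − 1.96) = 9% | 0.99 |
| Air, each age group | 8 | 0.4 | Φ(0.947 − 1.96) = 16% | 0.85 |
| Air, overall | 16 | 0.3 | Φ(1.116 − 1.96) = 20% | 0.65 |

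Rounding 12.5 to 12 or 13 gives 46% or 50%; rounding 37.5 to 37 or 38 gives 70% or 71%.

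**Sensitivity to alpha.** With 1.645 in place of 1.96 (one-sided 5%), surface power is 60% (hospital sub-group), 80% (age group) and 84% (overall). Air power is 15%, 24% and 30%.

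**Sensitivity to serial sampling.** Section 10 implies 4 sampling days per adult and 6 per child. Approximate the effective n as patients × T/(1 + (T−1)p), where T is the number of sampling days and p is the product of the two within-patient correlations. The protocol gives no p, so it is an assumption: p=1 returns the patient count and p=0 the count of patient-days.
- Surfaces overall range from 75 (p=1) to 375 (p=0: 12.5×4 + 12.5×6 + 25×4 + 25×6). At p=0.5 the figure is 20 + 21.4 + 40 + 42.9, about 124, against 85 needed.
- Hospital surface sub-groups at p=0.5 are 50/2.5 = 20 (adults) and 75/3.5 = 21.4 (children), against 24 needed. They reach 80% only if p is below about 0.38 and 0.44 respectively.
- Air overall ranges from 16 (p=1) to 80 (p=0: 8×4 + 8×6). At p=0.5 it is 2×6.4 + 2×6.9, about 27. The need is 85.

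**The case against.** Several points on the other side stand.

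- **Home sub-groups.** Section 10 counts all 25 patients in each home group for surface swabs, so two of the four sub-groups have the stated power. A reader might infer that none of the correlations is adequately powered; the documents do not support that.
- **Shedding duration.** Section 11 has a second quantified justification, adults against children with 50 per group. It relies on nasal swabs, which are planned for every patient, so the environmental restriction does not touch it. It would be wrong to say that the whole sample size lacks support.
- **Household illness.** The protocol expects that "other members of a household may well develop symptoms". One might infer that the 75 will shrink. But section 10 says that sampling of the index case and surfaces then continues, with everyone's symptoms recorded. Attribution to the index case weakens; the count does not fall for this reason.
- **Alpha.** None is stated for the correlations. At one-sided 5% the pooled surface tiers reach about 80% and 84%. Hospital surface sub-groups and air stay short at one pair per patient.
- **Serial data.** Objective (ii) speaks of serial shedding, and a model with random effects is planned, so one pair per patient is the worst case. This could restore the pooled surface tiers and, if within-patient correlation is low, the hospital ones. But the power statement counts patients and uses no such model. For air overall, even fully independent days give 80 against 85 at two-sided 0.05. In that extreme the children's air tiers would just reach their targets (24 against 24, and 48 against 47) and the adults' would not (16 against 24, and 32 against 47). Overall air would pass only with a one-sided test as well (68 needed).
- **Interpretation.** No rule in the protocol says that a null correlation will be read as no relation, and section 10 is open about the limited air coverage. The risk is misreading, not a planned false conclusion.

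**Conclusion.** Wrong as written. The power arithmetic is correct; the fault is that enrolled numbers stand in for patients with environmental data. At one pair per patient and two-sided 0.05, the shortfall is severe for the hospital surface sub-groups (48% against a claimed >80%) and for every air correlation (9% to 20%). It is modest for pooled surfaces (70% and 75%), where the detectable correlation moves only from 0.40 to 0.44 and from 0.30 to 0.32. The home surface sub-groups are as stated.

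The result rests on the protocol's own estimate that half of hospital patients are in side rooms, on its aim of 16 air patients, and on the assumed alpha. The pooled surface result is the least certain, because a one-sided test or use of the serial pairs could bring it to 80%. The possible laboratory rules in section 10, such as processing environmental swabs only when nasal load is high, would reduce the usable pairs further if adopted.

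**What to change.** In section 11 and the Synopsis, state alpha and sidedness for the correlations and replace the single sentence with power by outcome at the evaluable n:

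- **Surfaces:** hospital sub-groups n about 12 (detectable r about 0.72); home sub-groups n=25 (r=0.55, still powered); age groups n about 37 (r about 0.44); overall n=75 (r about 0.32).
- **Air:** n=4, 8 and 16 (r about 0.99, 0.85 and 0.65).

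Name the home sub-group and pooled surface correlations as those with 80% power at these values. Label hospital sub-group surface correlations and all air correlations descriptive, reported with confidence intervals. If the serial pairs are to support a better figure, state the within-patient correlations assumed. Leave the shedding-duration paragraph as it is.

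The cost is rewording one paragraph in two places and a less favourable stated power. No extra patients, samples or procedures are needed.

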FLU-CIN is an acronym for the newly formed Influenza (flu) Clinical Information Network funded by the Department of Health, England. When the swine influenza crisis began, the Department of Health and the Scientific Advisory Group for Emergencies considered it essential that a system was put in place rapidly to gain as full an understanding as possible of the most serious effects of the virus, and the effectiveness of different methods of treatment for those effects.

This means collecting information rapidly on the clinical condition and treatment of any patients hospitalised as a result of pandemic influenza. Cases are likely to appear in four main areas – adult medicine including infectious diseases and respiratory medicine; children's services; maternity services; and intensive care. Provisional guidelines for the clinical management of patients with an influenza-like illness during an influenza pandemic have been drawn up by the British Infection society, the British Thoracic Society and the Health Protection Agency in collaboration with the Department of Health. FLU-CIN will provide data which will allow revision of those guidelines in the light of emerging information specific to swine influenza.

Hospital cases will be identified from participating FLU-CIN centres in the East Midlands (Nottingham and Leicester) and South Yorkshire (Sheffield). These hospitals form three of five pilot centres for the network. They have the advantage of being close to the co-ordinating centre for this proposal, and will be staffed by DH funded Support Nurses whose job it will be to identify early, patients admitted with pandemic influenza.

Recruitment targets at these sites; Nottingham - 9 adults and 25 children Sheffield – 8 adults Leicester – 8 adults

We recognise that some patients are likely to have been ill for a period of time before being admitted to hospital and therefore may have passed their peak of viral shedding. Nevertheless some patients may well have deteriorated relatively quickly and patients requiring hospital admission usually have more severe disease. In all probability this may lead to a higher viral load and slower decline in virus shedding than in community patients and healthcare workers will be heavily and closely exposed to such patients. Thus we are firmly of the opinion that viral shedding data in this group of patients will still be of significant value.

COMMUNITY CASES:

We plan to recruit via 3 sources;

1. Local Media

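### The comparisons of mean shedding duration (children vs adults, mild vs severe) are described without a term for the other recruitment factor, although the study recruits by age and setting and expects setting to affect shedding

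*Protocol*

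**What the plan says.** Section 11 (Proposed Sample Size) sets the recruitment: "We will aim to recruit groups of about 25 patients with recent onset H1N1 influenza in each of the four main sub-groups". Section 9 (Cases) defines those sub-groups as hospitalised adults, hospitalised children, adults at home and children at home, which is an age-by-setting layout.

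For duration of shedding, Section 11 works "by pooling data into adults vs. children (n=50 per group") and states that "differences of 5 days (adults) vs. 6 days (children") can be detected with more than 80% power in a two-tailed test, "provided that the coefficient of variation in shedding was 0.3 or less". For 5 versus 7 or 5 versus 8 days it says that "the study is well powered to coefficients of variation up to 0.6", with no percentage.

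Under Statistical Analysis, the second stage will "compare the mean duration of shedding among children and adults as well as among mild and severe cases". The secondary objectives identify mild illness with community patients and more severe disease with hospitalised patients, so the second of these contrasts is the setting contrast. The third stage adds a survival analysis of predictors of duration.

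On hospital cases, Section 9 (Recruitment) says that "this may lead to a higher viral load and slower decline in virus shedding than in community patients".

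**The concern.** The protocol recruits by two factors because it expects both to matter, and it says which way setting should act on shedding. It then describes two comparisons of means that each collapse over the other factor. Two things follow if the tests are carried out as described.

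- **Power.** Half of each age group is hospital and half community. Any setting difference then sits in the residual variance of the adult-child test, although the design could remove it.
- **Validity.** The cells are only approximate in size. The 25 hospital children are all to come from Nottingham, while the hospital adults are spread over three sites (9, 8 and 8). If the cells fill unevenly, the hospital share differs between adults and children, and part of the setting difference passes into the age contrast.

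The adult-child comparison is the only duration contrast that Section 11 gives power for. The sentence also does not say whether the CV of 0.3 is the total CV in a pooled age group or the CV within a recruitment cell, and the effect on power depends on which is meant.

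**Working it through.** **Inputs from the protocol.** n = 50 per age group; 25 per cell; means 5 vs 6, 5 vs 7 and 5 vs 8 days; CV 0.3 or 0.6; two-tailed.

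**Assumed, because the protocol does not give them.** Alpha 0.05; SD = CV × mean; hospital-community difference D of 0 to 3 days, equal in adults and children.

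**1. The protocol's own figure (5 vs 6 days, CV 0.3).**
- SDs are 0.3 × 5 = 1.5 and 0.3 × 6 = 1.8.
- Average variance is (2.25 + 3.24)/2 = 2.745, so the SD is 1.657.
- SE = 1.657 × √(2/50) = 0.331, and 1/0.331 − 1.96 = 1.06. Power is 85.5% by the normal formula and 84.8% by Welch t.
- The claim of more than 80% is confirmed. It holds up to a CV of about 0.32.

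**2. Setting difference, CV 0.3 read as within-cell, 25 in every cell.** If setting is ignored, the variance that the test estimates is about 2.745 + D²/4. That gives 2.995, 3.745 and 4.995 for D = 1, 2 and 3. Putting these in the normal formula gives 82%, 73% and 61%. This slightly overstates the loss, because the 25:25 mix is fixed: D inflates the estimated SE but not the true variability of the mean difference. Simulation with cells fixed at 25 gives:

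| Assumed D (days) | Pooled Welch t | Adjusted for setting |
|---|---|---|
| 0 | 85% | 85% |
| 1 | 83% | 85% |
| 2 | 75–76% | 85% |
| 3 | 63% | 85% |

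The pooled test reaches about 80% at D = 1.5. The age estimate is unbiased in every row.

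**3. CV 0.3 read as the total CV of the pooled group.** The setting spread is then already inside the 0.3, and the pooled normal-formula figure stays at 85.5% for any D. Removing D²/4 from the variance by stratifying raises it to 88.6% at D = 1 and 96.6% at D = 2.

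**4. Unequal cells.** Bias of the pooled contrast = D × (hospital share in children − hospital share in adults). Example, both values assumed: 18 hospital children, the other cells at 25, D = 2.
- Bias = 2 × (18/43 − 25/50) = 2 × (0.419 − 0.500) = −0.16 day.
- The pooled estimate averages 0.84 instead of 1.0 day. Simulated power is 54% pooled and 82% adjusted, and the adjusted estimate averages 1.0.
- With D = 0 and the same cells, adjusted power is no lower than pooled power (both about 82%).

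**5. Larger differences at CV 0.6.**
- 5 vs 7: SDs 3.0 and 4.2, average variance (9 + 17.64)/2 = 13.32, SD 3.650, SE 0.730, and 2/0.730 − 1.96 = 0.78. Power is 78.2% (normal) or 77.3% (Welch t). With Welch t, 80% is reached up to CV 0.58. On the log scale the figure is 85.9%.
- 5 vs 8: SDs 3.0 and 4.8, average variance 16.02, SD 4.002, SE 0.800. Power is 96%.

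**The case against.** The strongest objection is that the protocol nowhere says the tests are unstratified. It names no test and neither states nor excludes a setting term. Adjustment covariates are often left to a statistical analysis plan, which is not at hand here. Pooling may only describe how 25 + 25 becomes 50, the paragraph calls the duration data mainly descriptive, and a survival analysis of predictors is planned. This stands to the extent that lack of stratification is an inference and not a stated choice. It does not remove the point: the protocol does describe the second-stage comparisons, each by a single factor. Predictors enter only in a separate third-stage analysis, which is not the comparison of means that was powered.

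A reader might infer that the power claim for 5 versus 6 days is wrong. It is not. The figure reproduces and is conditional on the CV. In a sentence about pooled groups, the total CV is a natural reading, and on that reading no power is lost.

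A reader might also infer that the age contrast is biased as planned. It is not: at 25 per cell the bias is zero, and nothing in the protocol predicts a shortfall in any one cell. The setting differences used above are assumptions too. Section 9 gives a direction but no size, and the loss is small unless the difference exceeds the 1-day age effect under test.

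On 5 versus 7 days, the protocol promises good power without a percentage, and the shortfall from 80% is small and depends on the method.

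**Conclusion.** The point holds as an improvement to the stated comparisons, not as an error in the sample size. Adjusting each duration comparison for the other recruitment factor is better under either reading of the CV. It restores about 85% power if 0.3 is a within-cell CV (against 83%, 75% and 63% pooled at assumed differences of 1, 2 and 3 days), and it raises power above 85% if 0.3 is the total CV. It also keeps the age contrast unbiased when the cells fill unevenly and the setting effect is similar in adults and children. These sizes rest on alpha 0.05, SD proportional to the mean, a common setting difference and, for the unequal-cell example, an assumed shortfall to 18.

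The statement on larger differences is sound for 5 versus 8 days (96%) and slightly generous for 5 versus 7 days at CV 0.6 (about 77% on the raw scale). That second item is minor.

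**What to change.** In Section 11 and the matching synopsis text:

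1. State that the adult-child comparison of mean duration is adjusted for, or stratified by, setting (hospital or community), and that the mild-severe comparison is adjusted for, or stratified by, age group. A two-way model or a stratified test would do.
2. Say whether the CV of 0.3 is the total CV in a pooled age group or the CV within a recruitment cell. The choice is the authors' to make; the power statement should match it.
3. Restate the larger differences: 5 versus 7 days has about 77% power at CV 0.6 on the raw scale, with 80% up to a CV of about 0.58; 5 versus 8 days has 96% at CV 0.6. If a log-scale analysis is intended, say so and give that figure.

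The cost is a few sentences and one degree of freedom per comparison. No change to recruitment, sampling or sample size is needed.
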